Section 1.3, Schedule of Activities	Day row was added to all subsections of the SoA.	To ensure clarity of day/week for scheduling purposes.
Section 1.3.1, Double-Blind Treatment Period	Verbal review at TC was added to the Participant Reminder Log: review/collect row.	Clarification of expectations during TC visits.
	Reference to Section 8.3.8 was added to the HIV, HBV, and HCV testing row.	Refer to rationale for change in Section 8.3.8.
	A separate row for HBV-DNA testing was added.	Refer to rationale for change in Section 8.3.8.
	TB testing note was shortened. Readers are directed to Section 8.3.6 and Section 5.2.	Note directing readers to updated TB testing information.

Section Number and Name	Description of Change	Brief Rationale
Section 1.3.2, Blinded Extension Period	Removed Week 54 scheduled time for conducting the Follow-up TC and added +7-day window.	Follow-up TC should be conducted 28 days after last dose of study intervention.
	Verbal review at TC was added to the Participant Reminder Log: review/collect row.	Refer to rationale for change in Section 1.3.1.
	A row for HBV-DNA testing was added.	Refer to rationale for change in Section 8.3.8.
Section 2.1, Study Rationale	Description of vitiligo disease activity was expanded.	Clarified definition of disease activity.
Section 4.1, Overall Design	Clarified that participants will stay in the study unless consent is withdrawn.	Updated for protocol consistency.
	Modified text to indicate that participants will alternate between placebo and MK-6194.	Placebo and MK-6194 are both considered study interventions.
	Modified the text to indicate that enrollment for the PK/PD/Biomarker sampling will be at least 15 participants per arm.	To avoid misunderstanding the number of subpopulation participants.
	Added definition of follow-up safety TC.	Refer to rationale for change in Section 1.3.2 regarding follow-up TC.
Section 4.2.1.3, Pharmacokinetic Endpoints	Modified the text to indicate that enrollment for the PK/PD/Biomarker sampling will be at least 15 participants per arm.	Refer to rationale for change in Section 4.1.
Section 4.2.1.4, Pharmacodynamic Endpoints	Modified the text to indicate that enrollment for the PK/PD/Biomarker sampling will be at least 15 participants per arm.	Refer to rationale for change in Section 4.1.

Section Number and Name	Description of Change	Brief Rationale
Section 4.2.1.6, Planned Exploratory Biomarker Research	Removed microbiome analysis.	Not applicable to this study.
Section 5.2, Exclusion Criteria	In exclusion criterion #12, HBV-DNA testing description was added, and the HCV definition was updated.	Refer to rationale for change in Section 8.3.8.
	Moved QuantiFERON-TB Gold testing guidance from criterion #13 to corresponding Section 8.3.6.	To clarify study entry guidance and initial TB retesting.
	In exclusion criterion #19, Table 1 Prohibited Medications, the 5-drug half-lives period of phototherapy was deleted.	Phototherapy does not have a half-life.
	A footnote was added to Table 1 Prohibited Medications to indicate that medications are prohibited until the last dose of study intervention is administered.	Updated to align with Sections 6.5 and 8.1.5.2.
Section 6.3.1, Intervention Assignment	Modified text to indicate that participants will alternate between placebo and MK-6194.	Refer to Section 4.1 rationale regarding study intervention.
Section 6.3.2, Stratification	Descriptions of stratification factors were expanded.	Updated to address investigator/site feedback.
Section 7.1, Discontinuation of Study Intervention	Added criterion for discontinuation if HBV-DNA is \geq LLOQ.	Refer to rationale for change in Section 8.3.8.
Section 8.1.1.3, Consent for PK/PD/Biomarker Subpopulation	Text added to indicate PK/PD/Biomarker consent will be collected at selected sites.	PK/PD/Biomarker testing is limited to selected sites.
Section 8.1.11, Participant Blinding/Unblinding	Added treatment unblinding guidance.	Inadvertently omitted during original protocol creation.
Section 8.1.13, PK/PD/Biomarker Subpopulation	Modified the text to indicate that enrollment for the PK/PD/Biomarker sampling will be at least 15 participants per arm.	Refer to rationale for change in Section 4.1.

Section Number and Name	Description of Change	Brief Rationale
Section 8.2.1, PROs	Added PROs timing and training information.	To harmonize with other sections of the protocol.
Section 8.3.2, Vital signs	HR and BP will be assessed similarly.	Corrected to avoid confusion.
	Added collection of vital signs timing exception.	Corrected a protocol inconsistency.
Section 8.3.6, TB Testing	Added TB testing guidance.	Refer for change in Section 5.2 regarding TB testing.
Section 8.3.7, Chest X-ray	Added the focus of chest x-rays is to identify TB.	Added as additional investigator guidance.
Section 8.10.2, Double-Blind Treatment Period	Added clarification regarding PROs administration.	Refer to rationale for change in Section 8.2.1.

1 PROTOCOL SUMMARY

1.1 Synopsis

Protocol Title: A Phase 2a, Multicenter, Randomized, Double-blind, Placebo-controlled Study to Evaluate the Efficacy and Safety of MK-6194 in Adult Participants with Non-Segmental Vitiligo

Short Title: MK-6194 in Adult Participants with Non-Segmental Vitiligo

Acronym: N/A

Hypotheses, Objectives, and Endpoints:

In adult participants with non-segmented vitiligo:

Primary Objective	Primary Endpoint
To evaluate the efficacy of MK-6194 on the percent change from baseline in Facial Vitiligo Area Scoring Index (F-VASI) at Week 24 H1: At least 1 MK-6194 dose is superior to placebo on percent change from baseline in Facial Vitiligo Area Scoring Index (F-VASI) at Week 24	F-VASI
To evaluate the safety and tolerability of MK-6194	AEs Discontinuation due to AEs
Secondary Objective	Secondary Endpoint
To evaluate the efficacy of MK-6194 on the percent change from baseline in Total Vitiligo Area Scoring Index (T-VASI) at Week 24	T-VASI

Overall Design:

Study Phase	Phase 2
Primary Purpose	Treatment
Indication	Vitiligo
Population	Adult participants with non-segmental vitiligo
Study Type	Interventional
Intervention Model	Parallel This is a multi site study.
Type of Control	Placebo
Study Blinding	Double-blind
Blinding Roles	Sponsor
	Investigator
	Participants or Subjects
Estimated Duration of Study	The Sponsor estimates that the study will require approximately 28 months from the time the first participant (or their legally acceptable representative) provides documented informed consent until the last participant's last study-related contact. Participants will take part in the study for 58 weeks. See Appendix 7 for country-specific requirements.

Number of Participants:

Approximately 165 participants will be randomized.

Intervention Groups and Duration:

Arm Name	Intervention Name	Unit Dose Strength(s)	Dosage Level(s)	Route of Administration	Regimen/ Treatment Period/ Vaccination Regimen	Use
MK-6194 Q2W	MK-6194	3 mg	3 mg	SC	Double-Blind Treatment and Blinded Extension Periods	Test Product
MK-6194 Q4W	MK-6194	3 mg	3 mg	SC	Double-Blind Treatment and Blinded Extension Periods	Test Product
MK-6194 Q4W	Placebo	0 mg	0 mg	SC	Double-Blind Treatment and Blinded Extension Periods	Placebo
Placebo Q2W	Placebo	0 mg	0 mg	SC	Double-Blind Treatment Period	Placebo

SC=subcutaneous; Q2W=every 2 weeks, Q4W=every 4 weeks

Note: To maintain the blind for MK-6194 Q4W, alternating placebo will be administered between the MK-6194 doses. Participants randomized to the placebo arm Q2W during the Double-Blind Treatment Period will be rerandomized to MK-6194 Q2W or MK-6194 Q4W during the Blinded Extension Period.

Other current or former name or alias for the study intervention is as follows: PT101.

Total Number of Intervention Groups/Arms	3
Duration of Participation	After a Screening period of up to 4 weeks, each participant will receive study intervention for approximately 52 weeks (24 weeks Double-Blind Treatment Period + 28 weeks Blinded Extension Period), followed by a safety follow-up telephone call 28 days after last study intervention is administered.

Study Governance Committees:

Executive Oversight Committee	Yes
Data Monitoring Committee	Yes
Clinical Adjudication Committee	No

[figure not shown]
Study Accepts Healthy Participants: No

A list of abbreviations is in Appendix 11.

1.2 Schema

The study design is depicted in Figure 1.

Figure 1 Study Design

IA= interim analysis; PBO= placebo; PK= pharmacokinetics; pts= participants; Q2W= every 2 weeks; Q4W= every 4 weeks; TC= telephone call; V= visit; Wk(s)= week(s)

1.3 Schedule of Activities

1.3.1 Double-Blind Treatment Period

	Screen	Double-Blind Treatment Period												Notes
Visit Number/Title:	1 Screen	2 Rand	3	4	5	TC	6	7	8	9	TC	10 ^a	Discon	
Scheduled Day/Week:	Up to 4 wks	Day 1 Wk 0	Day 2	Wk 2	Wk 4	Wk 6	Wk 8	Wk 12	Wk12 +1d	Wk 18	Wk 20	Wk 24		
Day		1	2	15	29	43	57	85	86	127	141	169		
Recommended Window			±12h	±3d	±3d	±3d	±7d	±7d	±12h	±7d	±3d	±7d		
Administrative Procedures														
Informed consent	X													
Informed consent for FBR	X													FBR consent is optional
IRT visit registration	X	X		X	X		X	X		X			X	
Medical history	X													
Prior/concomitant medications	X	X		X	X	X	X	X		X	X	X	X	
Inclusion/exclusion criteria	X	X												
Participant identification card	X	X												Add Randomization number to card at Visit 2.
IRT randomization		X												
Study intervention dispense/return		X		X	X		X	X		X		X	X	Dispense at Wks 2-18; return at all visits. Assess compliance of returned syringe(s).
SC injection: train/retrain participant on self-administration		X		X										Self-administration is preferable. Retrain as necessary. See Section 8.1.9.3.
SC injection: witnessed dose		X		X				X						Study staff to ensure proper self-administration. technique. See Section 8.1.9.4.

	Screen	Double-Blind Treatment Period												Notes
Visit Number/Title:	1 Screen	2 Rand	3	4	5	TC	6	7	8	9	TC	10 ^a	Discon	
Scheduled Day/Week:	Up to 4 wks	Day 1 Wk 0	Day 2	Wk 2	Wk 4	Wk 6	Wk 8	Wk 12	Wk12 +1d	Wk 18	Wk 20	Wk 24		
Day		1	2	15	29	43	57	85	86	127	141	169		
Recommended Window			±12h	±3d	±3d	±3d	±7d	±7d	±12h	±7d	±3d	±7d		
Participant Reminder Log: train/dispense		X		X	X		X	X		X				For recording study intervention administration, any complaints/illnesses, and any new medications taken between study visits.
Participant Reminder Log: review/collect				X	X	X	X	X		X	X	X	X	To be reviewed for accuracy. Verbal review at TC. See Section 8.1.9.5.
Dosing reminder telephone call						X					X			Additional reminders as necessary per site
Efficacy Procedures														PROs to be completed in order listed, before laboratory tests or other safety or efficacy procedures
VitiQoL Instrument		X						X				X	X	
VNS								X				X	X	
Patient Global Impression of Severity		X						X				X	X	
Patient Global Impression of Change/Meaningfulness								X				X	X	
Clinical Global Impression of Severity		X						X				X	X	
Clinical Global Impression of Change								X				X	X	
F-VASI	X	X		X	X		X	X		X		X	X	
T-VASI	X	X			X			X		X		X	X	
CCI														

	Screen	Double-Blind Treatment Period												Notes
Visit Number/Title:	1 Screen	2 Rand	3	4	5	TC	6	7	8	9	TC	10 ^a	Discon	
Scheduled Day/Week:	Up to 4 wks	Day 1 Wk 0	Day 2	Wk 2	Wk 4	Wk 6	Wk 8	Wk 12	Wk12 +1d	Wk 18	Wk 20	Wk 24		
Day		1	2	15	29	43	57	85	86	127	141	169		
Recommended Window			±12h	±3d	±3d	±3d	±7d	±7d	±12h	±7d	±3d	±7d		
Other Procedures														
Photography (face)	X	X					X	X				X	X	If baseline photographs are sufficient, photographs at Randomization are not required. See Section 8.2.3.
Photography (total body)	X	X						X				X	X	If baseline photographs are sufficient, photographs at Randomization are not required. See Section 8.2.3.
CCI														
Safety Procedures														
Height	X													
Weight	X											X	X	
Vital signs	X	X		X	X		X	X		X		X	X	Taken after completion of PROs and before blood samples collection
Full physical examination	X											X	X	
Directed physical examination		X		X	X		X	X		X				Per institutional standards, consistent with local requirements
12-lead ECG	X													Locally read
Chemistry	X				X		X	X		X		X	X	
Hematology	X			X	X		X	X		X		X	X	

	Screen	Double-Blind Treatment Period											Discon	Notes
Visit Number/Title:	1 Screen	2 Rand	3	4	5	TC	6	7	8	9	TC	10 ^a		
Scheduled Day/Week:	Up to 4 wks	Day 1 Wk 0	Day 2	Wk 2	Wk 4	Wk 6	Wk 8	Wk 12	Wk12 +1d	Wk 18	Wk 20	Wk 24		
Day		1	2	15	29	43	57	85	86	127	141	169		
Recommended Window			±12h	±3d	±3d	±3d	±7d	±7d	±12h	±7d	±3d	±7d		
Urinalysis (with microscopy)	X											X	X	To be performed at additional visits if clinical symptoms suggestive of UTI
Serum pregnancy test (hCG; POCBP only)	X													
FSH- (PONCBP only)	X													To confirm postmenopausal status. See Section 10.5.1.
Local urine pregnancy test (POCBP only)		X			X		X	X		X		X		Administered predose. If a urine test cannot be confirmed as negative (eg, an ambiguous result), serum test is required. See Appendix 7 for country-specific requirements.
TSH	X													
HIV, HBV, and HCV testing	X													See Section 8.3.8 to determine if further testing is needed. See Appendix 7 for country-specific requirements.
HBV-DNA testing	X							X				X	X	Only for participants with positive HBcAb and HBV-DNA <LLOQ at Screening.
TB testing	X													QFT TB Gold test or equivalent. See Section 8.3.6 and Section 5.2 (exclusion criterion #13).

	Screen	Double-Blind Treatment Period												Notes
Visit Number/Title:	1 Screen	2 Rand	3	4	5	TC	6	7	8	9	TC	10 ^a	Discon	
Scheduled Day/Week:	Up to 4 wks	Day 1 Wk 0	Day 2	Wk 2	Wk 4	Wk 6	Wk 8	Wk 12	Wk12 +1d	Wk 18	Wk 20	Wk 24		
Day		1	2	15	29	43	57	85	86	127	141	169		
Recommended Window			±12h	±3d	±3d	±3d	±7d	±7d	±12h	±7d	±3d	±7d		
Chest X-ray	X													Posterior-anterior chest x-ray. Locally read. See Section 8.3.7.
AE/SAE review	X	X		X	X	X	X	X		X	X	X	X	
PK/PD/Biomarkers (All participants)														
Blood for serum ADA		X		X	X			X				X	X	Samples for ADA and PK should be drawn at the same time predose
Blood for serum PK		X	X	X	X			X	X			X	X	CCI [REDACTED]
Blood for genetic analysis		X												Predose from randomized participants only, See Section 8.8.1.
Blood for DNA analysis		X			X			X				X	X	Leftover sample will be stored for FBR. See Section 8.9.
Blood for immunophenotyping	X	X			X			X				X	X	See Section 8.7.2

	Screen	Double-Blind Treatment Period												Notes
Visit Number/Title:	1 Screen	2 Rand	3	4	5	TC	6	7	8	9	TC	10 ^a	Discon	
Scheduled Day/Week:	Up to 4 wks	Day 1 Wk 0	Day 2	Wk 2	Wk 4	Wk 6	Wk 8	Wk 12	Wk12 +1d	Wk 18	Wk 20	Wk 24		
Day		1	2	15	29	43	57	85	86	127	141	169		
Recommended Window			±12h	±3d	±3d	±3d	±7d	±7d	±12h	±7d	±3d	±7d		
Blood for serum biomarkers analysis		X			X			X				X	X	Leftover sample will be stored for FBR. See Section 8.9.
Blood for RNA analysis		X						X				X	X	Leftover sample will be stored for FBR. See Section 8.9.
ADA= antidrug antibodies; AE= adverse event(s); d= day; Discon= discontinuation; DNA= deoxyribonucleic acid; EC=Ethics Committee; ECG= electrocardiogram; FBR= Future Biomedical Research; FSH= follicle-stimulating hormone; F-VASI= Facial Vitiligo Area Scoring Index; h= hour; HBcAb= hepatitis B core antibody; HBV= hepatitis B virus; HCV= hepatitis C virus; hCG= human chorionic gonadotropin; HIV= human immunodeficiency virus; IRB= Institutional Review Board; IRT= interactive response technology; LLOQ= lowest limit of quantitation; PD= pharmacodynamics; PK= pharmacokinetics; POCBP= Participant of childbearing potential; PONCBP= Participant of nonchildbearing potential; PROs=participant reported outcomes; Q2W= every 2 weeks; QFT= QuantiFERON; QoL= quality of life; Rand= randomization; RNA= ribonucleic acid; SAE= serious adverse event(s); SC= subcutaneous; TB= tuberculosis; TC= telephone call; TSH= thyroid-stimulating hormone; T-VASI= Total Vitiligo Area Scoring Index; UTI= urinary tract infection; V=visit; CCI ; VitiQoL= Vitiligo Quality of Life Instrument; VNS= Vitiligo Noticeability Scale; Wk(s)= Week(s).														

(a) Procedures for the Blinded Extension portion of this visit are in Section 1.3.2.

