Has a negative highly sensitive pregnancy test (urine or serum) as required by local regulations within 24 hours (for a urine test) or 72 hours (for a serum test) before the first dose of study intervention. If a urine test cannot be confirmed as negative (eg, an ambiguous result), a serum pregnancy test is required. In such cases, the participant must be excluded from participation if the serum pregnancy result is positive. Additional requirements for pregnancy testing during and after study intervention are in Section 8.3.5.

Abstains from breastfeeding during the study intervention period and for at least 28 days after study intervention MK-6194 is last administered.

Medical history, menstrual history, and recent sexual activity has been reviewed by the investigator to decrease the risk for inclusion of a POCBP with an early undetected pregnancy.

Informed Consent

10. The participant (or legally acceptable representative) has provided documented informed consent for the study. The participant may also provide consent for FBR. However, the participant may participate in the study without participating in FBR. See Appendix 7 for country-specific requirements.

Additional Categories

11. Is willing and considered able by the investigator to comply with study procedures, including adherence with study intervention, visit schedule, and completion of PROs. Participant must be able to read, understand, and complete the PROs.

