7.2 Participant Withdrawal From the Study

A participant must be withdrawn from the study if the participant or participant’s legally acceptable representative withdraws consent from the study.

If a participant withdraws from the study, they will no longer receive study intervention or be followed at scheduled protocol visits.

Specific details regarding procedures to be performed at the time of withdrawal from the study, as well as specific details regarding withdrawal from FBR, are outlined in Section 8.1.10. The procedures to be performed should a participant repeatedly fail to return for scheduled visits and/or if the study site is unable to contact the participant are outlined in Section 7.3.

A participant or participant’s legally acceptable representative who consented for the Subpopulation procedures, may withdraw consent for the additional PK/PD/Biomarker sample collection. Specific details regarding activities to be performed at the time of withdrawal from the Subpopulation procedures are outlined in Section 8.1.10.2. Withdrawal from the Subpopulation does not represent withdrawal from the main study.

See Appendix 7 for country-specific requirements.

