8.1.10 Discontinuation and Withdrawal

Participants who discontinue study intervention before completion of the treatment period will have a Discontinuation Visit and should be encouraged to continue to be followed for all remaining study visits until the end of the study period in which they discontinued as outlined in the SoA and Section 8.10.5.

Participants who withdraw from the study should be encouraged to complete all applicable activities scheduled for the Discontinuation Visit at the time of withdrawal. Any AEs that are present at the time of withdrawal should be followed in accordance with the safety requirements outlined in Section 8.4.

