8.3.5 Pregnancy Testing

Pregnancy testing:

- Pregnancy testing requirements for study inclusion are described in Section 5.1.
- Pregnancy testing (urine and/or serum) should be conducted as per SoA at the specified visits during intervention. A negative pregnancy test should be confirmed prior to administration of study intervention.
- Additional serum or urine pregnancy tests may be performed, as determined necessary by the investigator or required by local regulation, to establish the absence of pregnancy at any time during the participant's participation in the study.

See Appendix 7 for country-specific requirements.

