8.4.5 Pregnancy and Exposure During Breastfeeding

Although pregnancy and infant exposure during breastfeeding are not considered AEs, any pregnancy or infant exposure during breastfeeding (spontaneously reported to the investigator or their designee) that occurs in a participant during the study are reportable to the Sponsor.

All reported pregnancies must be followed to the completion/termination of the pregnancy.

Any pregnancy complication will be reported as an AE or SAE.

The medical reason (example: maternal health or fetal disease) for an elective termination of a pregnancy will be reported as an AE or SAE. Prenatal testing showing fetus will be born

with severe abnormalities/congenital anomalies that leads to an elective termination of a pregnancy will be reported as an SAE for the fetus.

Pregnancy outcomes of ectopic pregnancy, spontaneous abortion, missed abortion, benign hydatidiform mole, blighted ovum, fetal death, intrauterine death, miscarriage, and stillbirth must be reported as serious events (Important Medical Events). If the pregnancy continues to term, the outcome (health of infant) must also be reported.

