8.10.4 PK/PD/Biomarker Subpopulation Visits

At selected sites, additional PK/PD/Biomarker samples will be collected from participants who consent as outlined in the SoA (Section 1.3.3) in addition to the activities listed in the Double-Blind Treatment and Blinded Extension Periods (Sections 1.3.1 and 1.3.2).

During Visit 2, an additional PK sample will be collected 2 to 10 hours after study intervention administration. Participants will need to remain at, or come back to, the site to have this sample collected. If the PK sample is not able to be collected at Visit 2, then the sample will be collected 2 to 10 hours after study intervention administration at Visit 7.

Participants who discontinue study intervention will no longer be part of this Subpopulation.

8.10.5 Participants Discontinued From Study Intervention but Continuing to be Monitored in the Study

Any participant who prematurely discontinues study intervention will have a Discontinuation Visit as outlined in the SoA (Section 1.3). Participants will be encouraged to continue their participation in the study off study intervention until the end of the study period in which they discontinued, and be followed for all remaining study visits in that period (Section 7.1) as outlined in the SoA with the following exceptions, which are not applicable after study intervention is discontinued.

- Efficacy data, including photographs
- PK, PD, Biomarker sample collection
- Study intervention dispense/return
- Witnessed dose
- Train/retrain participant on self-administration
- Dosing reminder telephone call

Discontinuation Visit assessments should be performed at the time of discontinuation. Any AEs present at the time of discontinuation should be followed in accordance with the safety requirements outlined in Section 8.4.

Concomitant therapies specifically prohibited (see Section 6.5, [\[Table 1\]](#), and Appendix 8) while the participant was on study intervention are no longer prohibited after discontinuation of study intervention, except for live vaccines. See Appendix 7 for country-specific requirements.

Note: At the Discontinuation Visit, IRT will be contacted for closeout purposes.

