8.10.6 Follow-up Telephone Call

Participants will be contacted at least 28 days (+7 days) after the last administration of study intervention to determine if any AEs have occurred since discontinuing study intervention. During this telephone call, AE and concomitant medication information will be collected.

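### Double-Blind Discontinuation Visit has no pregnancy test, so outside Argentina a participant of childbearing potential who leaves there, between test visits, has no scheduled test after the last dose

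*Protocol*

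**What the plan says.** Protocol 1.3.1 lists "Local urine pregnancy test (POCBP only" at Visits 2, 5, 6, 7, 9 and 10 (Weeks 0, 4, 8, 12, 18 and 24). The Discontinuation cell of that row is empty. The serum test is at Screening only. In 1.3.2 the urine test is marked at Visits 12 to 16 and at Discontinuation.

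The text around the schedule says:

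- **5.1, criterion 9:** "Additional requirements for pregnancy testing during and after study intervention are in Section 8.3.5".
- **8.3.5:** testing follows the schedule during intervention. Beyond that, "Additional serum or urine pregnancy tests may be performed, as determined necessary by the investigator or required by local regulation".
- **8.1.10:** "Participants who withdraw from the study should be encouraged to complete all applicable activities scheduled for the Discontinuation Visit at the time of withdrawal".
- **7.2:** "If a participant withdraws from the study, they will no longer receive study intervention or be followed at scheduled protocol visits".
- **8.10.5** (stopping drug but not the study): "Participants will be encouraged to continue their participation in the study off study intervention until the end of the study period". Pregnancy testing is not among the procedures dropped for these participants.
- **8.10.6** (28-day call): "During this telephone call, AE and concomitant medication information will be collected".
- **8.4.5:** what must be reported is "any pregnancy or infant exposure during breastfeeding (spontaneously reported to the investigator or their designee) that occurs in a participant during the study".
- **Appendix 7:** Argentina requires monthly tests and one at the end of study intervention. The Czech Republic requires a test every 30 days during treatment.

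**The concern.** The two periods treat the same event differently, and no reason is given. Someone who leaves during the Extension is tested at the exit visit; someone who leaves during the Double-Blind period is not. Criterion 9 sends the reader to 8.3.5 for testing after study intervention, but 8.3.5 contains no such requirement.

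The protocol treats pregnancy as a serious matter. Contraception is required for at least 28 days after the last dose (5.1), pregnancies must reach the sponsor within 24 hours of being learned of (Table 3), and each is followed to its end (8.4.5). All of this depends on detection. For a participant who leaves at this visit, a pregnancy begun since the last scheduled test comes to light only if the investigator chooses to test or the participant reports it.

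**Working it through.** The plan states no figure on this point, so the check has three parts: the schedule cells, the other text that might supply a test, and the size of the gap.

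**1. The cells.** The 1.3.1 pregnancy row has its full set of 14 cells, so the blank is not a shifted column. The urinalysis and HBV-DNA rows in the same block also have 14 cells, and both are marked at Discontinuation. The 1.3.2 row has all 11 cells and is marked at Discontinuation. Among the unredacted rows of 1.3.1, the pregnancy test is the only one marked at Week 24 but not at Discontinuation. The directed physical examination is blank at Discontinuation in both periods because the full examination replaces it.

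The note that the test is given before dosing does not explain the blank. The Extension row has the same note, yet the test is marked at Discontinuation and at Week 52, when no dose is given (4.1).

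**2. Other sources of a test.**

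| Source | Scheduled test for someone who leaves at this visit? |
|---|---|
| 8.3.5 | No: refers back to the schedule; otherwise discretion or local regulation |
| 8.1.10 and 7.2 | No: only the activities scheduled for Discontinuation, then no more scheduled visits |
| 8.10.6 | No: adverse events and medications only |
| 8.10.5 | Only if the participant stays for the remaining visits |
| Appendix 7, Argentina | Yes, at end of study intervention |
| Appendix 7, Czech Republic | No: shorter gap during treatment, nothing at discontinuation |

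**3. Size of the gap.** Inputs are test visits at Weeks 0, 4, 8, 12, 18 and 24 (before dosing) and doses every 2 weeks from Week 0 to Week 22. The Week 24 dose belongs to the Extension (8.10.2). That gives 22/2 + 1 = 12 possible last doses. The table assumes the participant leaves before the next test visit.

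| Last dose (week) | Last scheduled test (week) | Doses at or after that test | Doses strictly after it | Tests after first dose |
|---|---|---|---|---|
| 0 | 0 | 1 | 0 | 0 |
| 2 | 0 | 2 | 1 | 0 |
| 4 | 4 | 1 | 0 | 1 |
| 6 | 4 | 2 | 1 | 1 |
| 8 | 8 | 1 | 0 | 2 |
| 10 | 8 | 2 | 1 | 2 |
| 12 | 12 | 1 | 0 | 3 |
| 14 | 12 | 2 | 1 | 3 |
| 16 | 12 | 3 | 2 | 3 |
| 18 | 18 | 1 | 0 | 4 |
| 20 | 18 | 2 | 1 | 4 |
| 22 | 18 | 3 | 2 | 4 |

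In all 12 rows no scheduled test follows the last dose. In 2 of 12 (last dose Week 0 or 2) no scheduled test follows even the first dose; in 10 of 12 at least one does.

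The age of the last test is bounded by the interval between test visits. Nominal test days are 1, 29, 57, 85, 127 and 169. The windows are none at Day 1, ±3 days at Day 29 and ±7 days afterwards.

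| Interval (weeks) | Nominal days | With windows at opposite extremes |
|---|---|---|
| 0 to 4 | 29 − 1 = 28 | 28 + 3 = 31 |
| 4 to 8 | 57 − 29 = 28 | 28 + 3 + 7 = 38 |
| 8 to 12 | 85 − 57 = 28 | 28 + 7 + 7 = 42 |
| 12 to 18 | 127 − 85 = 42 | 42 + 7 + 7 = 56 |
| 18 to 24 | 169 − 127 = 42 | 42 + 7 + 7 = 56 |

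**The case against.** The strongest reply is that the gap is real but narrow. The default path after stopping drug is to stay for the remaining visits of the period, where the scheduled tests still apply. If the participant stops at a visit that has its own test, such as attending Week 8 undosed after a last dose at Week 6, that test covers them. Those who withdraw are only encouraged to complete the Discontinuation Visit, so a mark in the schedule cannot guarantee a test.

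The 42- and 56-day figures are the schedule's ordinary test intervals, which also apply to participants who continue dosing. They are upper limits that an earlier exit would not reach. A dose given on the same day as a negative predose test is also less worrying; strictly after the last test there are 0 to 2 doses, not 1 to 3.

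The expected number of pregnancies is small. The planned 15% dropout is 0.15 × 165 ≈ 25 people. If all were of childbearing potential, all left, and all had a 42-day gap, the required contraceptive failure rate of under 1% per year gives fewer than 25 × 0.01 × 42/365 ≈ 0.03 pregnancies. At an assumed 10% per year it would be about 0.3. Both overstate, because the 25 would include people who cannot become pregnant. Finally, no dosing decision depends on the result, since drug has already stopped, and adverse event review and discretionary testing remain.

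All of this limits the size of the point and stands as such. None of it supplies a scheduled test for the participants described or explains why the two periods differ. Reporting duties and discretionary tests do not replace a scheduled one.

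**Conclusion.** The concern holds. Outside Argentina, a participant of childbearing potential who leaves the study at a Double-Blind Discontinuation Visit before the next test visit has no scheduled pregnancy test after the last dose, whichever of the 12 doses was last. The last test may be up to about 6 weeks old, or 8 weeks at the window limits.

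This rests on the schedule as printed and on dosing every 2 weeks as planned. It does not apply to participants who stay for later visits or whose discontinuation falls at a test visit. The documents do not give the number affected, and it is likely to be small. The matter is one of participant safety and pregnancy follow-up; endpoints, estimand and power are not affected. It merits correction because the sponsor already tests at the same point in the Extension and the change costs very little.

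**What to change.** Mark the local urine pregnancy test in the Discontinuation column of 1.3.1, as in 1.3.2. Add one sentence to 8.3.5 stating that participants of childbearing potential are tested at the Discontinuation Visit in both periods; this also partly repairs the cross-reference from criterion 9.

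The cost is one cell, one sentence and one local urine test per affected participant, at a visit where urinalysis is already scheduled. The change does not detect conception later in the 28-day contraception window, which the Extension schedule does not cover either.
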